Telephone follow-up at one week and one month:

1. Hospital readmission rate
2. Days missed of school for patient
3. Days missed of work for parent/guardian
4. Number of emergency room visits for asthma symptoms since discharge
5. Number of physician office visits for asthma symptoms since discharge
6. Number of recurrences of asthma symptoms since discharge
7. Number of courses of oral steroids since discharge (only at 1 month follow-up)

Also monitored: Respiratory viral panel or rapid viral testing results (if obtained as part of medical care), chest x-ray results (if obtained as part of medical care), medication side effects (diarrhea, abdominal pain, vomiting, flatulence), transfer to intensive care unit, time of wean of beta-agonists (q3h and q4h), and asthma severity (PASS score) at time of enrollment

“Mechanism Subset Study”: A Pilot and Feasibility Study in the subset of patients who consent to sample retrieval:

- Nasopharyngeal aspirate samples on enrollment and at 48 hours – measure a set of select biomarkers associated with inflammation (including IL-8) via Bioluminex or ELISA technology, eosinophil and neutrophil count per high power field, Mycoplasma and Chlamydia PCR

[figure not shown]
- Serum on enrollment and at 48 hours – measure same biomarkers of inflammation as in above aspirate, Mycoplasma and Chlamydia IgM and IgG, Mycoplasma and Chlamydia PCR, absolute neutrophil and eosinophil count

METHODS

Population

The study will include patients between the ages of 4-12 years of age admitted to the pediatric inpatient unit or pediatric intensive care unit at the Children's Hospital at Montefiore (CHAM).

Inclusion Criteria: Patients will be considered for enrollment if 4-12 years of age with an admission diagnosis of asthma and a history of persistent asthma (as defined by National Heart, Lung, and Blood Institute; see below and Eligibility Questionnaire).

Key: Alphabetical order is used when more than one treatment option is listed within either preferred or alternative therapy. ICS, inhaled corticosteroid; LABA, inhaled long-acting beta₂-agonist, LTRA, leukotriene receptor antagonist; SABA, inhaled short-acting beta₂-agonist

Notes:

- The stepwise approach is meant to assist, not replace, the clinical decisionmaking required to meet individual patient needs.
- If alternative treatment is used and response is inadequate, discontinue it and use the preferred treatment before stepping up.

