Prolongation of expiration (= ratio of the length of expiration over inspiration)	Normal/mild prolongation	Moderate prolongation	Severe prolongation

Other than the administration of azithromycin suspension or placebo, the medical treatment of the enrolled patients will be at the discretion of the medical team. The current standard of care for treatment of acute asthma exacerbations in hospitalized children includes inhaled beta-agonists and systemic steroids. The medical team often continues or initiates "controller" asthma medications during the inpatient stay (ie inhaled corticosteroids, leukotriene receptor antagonists). In addition, patients with severe asthma might receive intravenous medications (ie magnesium sulfate, terbutaline, aminophylline). No medical treatments will constitute exclusion from the study. However, invasive or non-invasive mechanical ventilatory support will be part of safety exit criteria.

At 7-10 days and again between 28 and 35 days after discharge, research personnel will contact the parent/guardian of enrolled patient for a follow-up interview. This interview will include questions about recurrence of asthma symptoms, days of work/school missed, hospital readmissions, emergency room visits, pediatrician visits, subsequent steroid courses, and medication side effects.

Mechanism Subset Study: A Pilot and Feasibility Study in a Subset of Patients

After enrollment, and at the time of the PASS asthma severity scoring, research personnel will ask parents/guardians if they would also be willing to participate in a separate subset study involving blood and nasal aspirate samples. If parents/guardians consent, they will be offered compensation for their time and inconvenience (if funding is available). If the parent/guardian is interested, the research personnel will obtain a separate, additional informed consent from the parent/guardian and assent from the child for the "Mechanism Subset Study". At that time, a nasal aspirate sample will be obtained by the research personnel (who will be trained on proper technique prior to the start of study). A blood sample will be obtained as soon as possible. A second sample of both blood and nasal aspirate will be obtained on the calendar day that is 48 hours from the first sample. Two samples will allow for baseline and post-treatment samples to be compared.

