The data from the interview questionnaire will be coded and descriptive statistics will be used to analyze the baseline characteristics of the two groups. If the parent characteristics are not balanced, multi-variable analysis will be utilized to adjust for variables not balanced by randomization. Secondary outcome measures will be compared using chi-squared test for categorical data and t-test or Mann-Whitney U test for continuous data, with statistical significance considered a p value < 0.05.

Due to the invasive nature of the sample collection in the "Mechanism Subset Study", only 25% of patients are expected to agree to submit to this portion of the study. These patients may not be representative of all patients in each arm of the study and will not be randomized. This subset study will be a pilot and feasibility study for future investigation into the potential mechanism of action of azithromycin in asthma. Data will be analyzed to compare the proportion of positive lab findings in each group using chi-squared analysis. There will not likely be sufficient power to find statistical significance, but the results will be used to estimate the effect size for subsequent study.

ETHICAL CONSIDERATIONS

Risks/Benefits

The potential risks are considered minimal. This study meets the category in the U.S. Department of Health and Human Services Code of Federal Regulations, Part 46, Subpart D (§46.405) for research involving greater than minimal risk but presenting the prospect of direct benefit to the individual subjects. The risks are deemed by the investigators to be justified by the anticipated benefit to the subjects; and the anticipated benefit is at least as favorable to the subjects as that presented by available alternative approaches.

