Patients will be recruited after identification by pediatric emergency room staff, admitting physician, or pediatric residents of patient with admission diagnosis of acute asthma exacerbation in the age range of 4-12 years. After the medical staff has determined if the parent/guardian is willing to meet with research personnel, the parent/guardian of the admitted child will be approached and undergo a standardized interview to determine if the patient meets eligibility requirements. If eligibility requirements are met, the research personnel will obtain informed consent from the parent/guardian and assent from the child (if applicable) for participation in the study.

The details of the study will be explained by research personnel and all questioned will be answered before consent and assent are obtained. Potential risks and benefits will be discussed. The parent/guardian will need to be physically present at the bedside of the child and written confirmation of consent will be obtained via signature on a consent form. For children 7-12 years of age capable of assent, assent will be obtained after verbal confirmation via signature of the child on an assent form.

For the “Mechanism Subset Study”: After enrollment, and at the time of the PASS asthma severity scoring, research personnel will ask parents/guardians if they would also be willing to participate in a subset study involving blood and nasal aspirate samples. If the parent/guardian is interested, the research personnel will obtain a second and separate informed consent from the parent/guardian and assent from the child (7-12 years) for the “Mechanism Subset Study”.

Adverse Event Monitoring

Adverse events that will be monitored include: bronchospasm or worsening clinical status (as determined by the primary medical team), transfer to the intensive care unit, medication side effects (abdominal pain, diarrhea, flatulence, vomiting), and readmission for asthma within 30 days. Additional unanticipated adverse events will also be monitored. Adverse events will be standardly documented and reported to the IRB within 30 days. All co-investigators and research personnel will immediately report any serious adverse events to the PI who will report them to the IRB within 48 hours.

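### Follow-up outcomes lack a fixed time window: the last call can fall before the 30-day readmission period ends, four counts stop on the day of the call, and missed days have no stated start

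*Combined protocol and SAP*

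**What the plan says.** Five places in the combined protocol and SAP bear on the follow-up window.

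- **Methods, Study Design:** families are interviewed "At 7-10 days and again between 28 and 35 days after discharge". The interview covers recurrence, missed days, readmissions, visits, steroid courses and side effects.
- **Outcome Measures, Secondary Outcomes:** the list is headed "Telephone follow-up at one week and one month". Four of its seven items are counted since discharge with no end day: emergency visits ("Number of emergency room visits for asthma symptoms since discharge"), office visits, recurrences and oral steroid courses. Steroid courses are asked at the second call only. The other three items are "Hospital readmission rate", "Days missed of school for patient" and the matching item for a parent's work; these name neither a start nor an end.
- **Adverse Event Monitoring:** one monitored event is "readmission for asthma within 30 days". Neither the start of the 30 days nor the data source is given.
- **Ethical Considerations, Risks/Benefits:** the hoped-for later benefits are placed in the month after the drug is given, which is a different origin from discharge.
- **Statistical Analysis:** "Secondary outcome measures will be compared using chi-squared test for categorical data and t-test or Mann-Whitney U test for continuous data". There is no fixed cut-off and no allowance for unequal observation time.

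No section provides for a repeat call or a record check after a second call made on day 28 or 29.

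**The concern.** There are three separate consequences.

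1. **Coverage.** A 30-day safety event is paired with an interview that may take place on day 28 or 29. If the call is the source and discharge is the origin, the last day or two are not observed.
2. **Unequal exposure.** A count that runs to the day of the call depends partly on when the family was reached, and the planned tests treat all children as observed equally long.
3. **Origin.** Discharge happens after randomisation, and it is the event azithromycin is hypothesised to bring forward. If missed days are counted from discharge, a child sent home sooner may spend at home days that would otherwise have been inpatient days. Those days would then count as missed school only in the arm with the shorter stay. Blinding does not prevent this, because it comes from the definition of the outcome.

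The third consequence matters most for interpretation: a real gain in length of stay could be accompanied by an apparent loss in missed days that only reflects where the recovery took place.

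**Working it through.** **The plan's own figures.** The target difference is 16/24 = 0.67 day, with SD 1.6. A two-sided t-test at 0.05 with 80% power needs 90.5, so 91 per group. The Mann-Whitney adjustments give 91 × π/3 = 95.3, so 96 (normal); 91 (uniform); and 91 × 9/π² = 82.98, so 83 (logistic). This matches the stated range of 83 to 96. Allowing for attrition, 96/0.90 = 106.7, so 107 per group, as stated. These figures concern length of stay and do not depend on the follow-up windows. The 107 is used below only as a denominator.

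**1. Coverage of 30 days from discharge.** The second window has 8 permitted days (28 to 35), and 2 of them precede day 30. If calls were spread evenly (assumption), 2/8 × 107 = 26.75, or about 27 children per arm, would be observed for less than 30 days. Mean unobserved time would be (2 + 1)/8 = 0.375 day.

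The documents give no readmission rate, so a 30-day risk R of 2%, 5% or 10% is assumed, with constant hazard h = −ln(1 − R)/30. The risk not seen by a call on day c is R − (1 − e^(−hc)).

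| Assumed R | Missed, day 28 | Missed, day 29 | Expected missed per 107, even spread | Per 107, all calls on day 28 |
|---|---|---|---|---|
| 2% | 0.00132 | 0.00066 | 0.03 | 0.14 |
| 5% | 0.00325 | 0.00163 | 0.07 | 0.35 |
| 10% | 0.00634 | 0.00317 | 0.13 | 0.68 |

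The even-spread column is 107 × (day-28 value + day-29 value)/8.

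**2. Unequal exposure.** The extremes between two children are 10/7 = 1.43 and 35/28 = 1.25. For a Poisson count with mean m at average exposure, the variance is inflated by 1 + m × CV², where CV is the coefficient of variation of exposure. With call days spread evenly:

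- days 7-10: mean 8.5, variance 1.25, CV² = 1.25/8.5² = 0.0173; inflation 1.017 at m = 1 and 1.035 at m = 2;
- days 28-35: mean 31.5, variance 5.25, CV² = 5.25/31.5² = 0.0053; inflation 1.005 at m = 1 and 1.016 at m = 3.

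The means are assumptions, since the documents give none. Lower means shrink the inflation further. Both windows are timed from discharge, so the length of the discharge-to-call interval does not depend on length of stay.

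**3. Missed days counted from discharge.** Suppose the full 0.67 day gained is spent at home and 5 of 7 days are school days. The active arm then gains at most 0.67 × 5/7 = 0.48 missed school days on average. If inpatient days are counted as missed, the same days appear in both arms and this mechanism largely disappears. For visits, recurrences and steroid courses, the size and direction of any shift cannot be computed from the documents.

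**4. Would a randomisation clock suit every outcome?** Use admission as a stand-in for randomisation and the planning mean stay of 3.0 days. A 30-day window then leaves 30 − 3.0 = 27.0 days at home in the control arm and 30 − 2.33 = 27.67 in an arm with the hypothesised benefit, a ratio of 1.025. For events that can occur only after discharge, that clock would itself give the arms different time at risk.

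**The case against.** The case against making much of this is good, and most of it stands.

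- A reader might infer that 30-day readmission cannot be known under this plan. The documents do not support that. The 30-day item is a monitored adverse event, separate from the readmission-rate outcome, and nothing says the call is its only source. Its origin is also unstated. If the 30 days run from administration, a day-28 call after a stay of 3.0 days falls near day 31 after admission and covers the period; it would fall short for stays under about 2 days.
- A reader might infer from the ratios 1.43 and 1.25 that the arms will be observed unequally. Those are extremes between individual children. Research staff and parents are blinded, so the day of the call should not differ systematically by arm.
- A reader might infer that earlier discharge necessarily raises the follow-up counts in an arm that works. That requires the drug to shorten stay without speeding recovery to match, whereas Risks/Benefits anticipates fewer days of symptoms as well. It also requires missed days to be counted from discharge, which the outcome list does not say.
- Discharge is the natural origin for readmissions and post-discharge visits, and moving every clock to randomisation would create a new imbalance.

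What remains is that no outcome has both an origin and an end day, the earliest permitted second call precedes the only stated 30-day limit if that limit runs from discharge, and the treatment of inpatient days in the missed-day items is left open.

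**Conclusion.** The point holds as a cheap improvement to secondary and safety outcomes.

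- **Coverage:** the stated schedule does not guarantee 30 days of observation after discharge, but the expected loss is below one readmission per arm even if every call fell on day 28. This assumes a 30-day risk of 2-10%, constant hazard, and the call as sole source.
- **Exposure:** the varying call day is noise of about 0.5-3.5% of variance at assumed means of 1-3, with calls spread evenly. It is not a between-arm bias.
- **Missed days:** a shift against the active arm is possible, with a ceiling of about 0.48 school days. It depends on a real length-of-stay effect, on return to school not being brought forward to match, and on counting from discharge. It is a risk left open by the definition, not a demonstrated bias.

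The primary outcome and the 107 per group are unaffected.

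**What to change.** 1. Make the second call on days 30-35 after discharge, and have both interviews record the dates of events.
2. Count readmissions, emergency visits, office visits and recurrences over fixed windows from discharge, to day 7 and to day 30. Count steroid courses to day 30 only. Keep discharge as the origin for these events.
3. Take same-hospital readmissions and emergency visits from the hospital database already searched for planning, assuming it can return both, and use the call for care elsewhere. This also covers families who cannot be reached. Since identifiers are to be destroyed as early as possible, the query has to be run first.
4. Count missed school and work days from randomisation to a fixed day, with inpatient days included. A call at day 30 or later after discharge always lies beyond day 30 after randomisation, so that end day is available for every child reached.
5. Reconcile the time origins in Secondary Outcomes, Study Design, Risks/Benefits and Adverse Event Monitoring, and state the fixed windows in Statistical Analysis.

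The cost is a second-call window two days shorter (6 permitted days, not 8), date fields on the questionnaire and one database query. Events after day 30 no longer count. The sample size does not change.

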At the Children’s Hospital at Montefiore (CHAM), the macrolide azithromycin is currently being used by some practitioners for its presumed anti-inflammatory effects in patients with acute asthma exacerbations. In 2010, 14% of 895 pediatric patients with a primary diagnosis of asthma received azithromycin during their inpatient stay. (Data obtained from a Clinical Looking Glass preliminary search). The length of stay of patients who received azithromycin was longer (mean: 4.5 days, median 3.8 days) than those who did not receive azithromycin (mean: 3.2 days, median 2 days) which may suggest that the current practice includes administering azithromycin to more severe asthma patients or patients refractory to standard treatments. A similar search of patients admitted with a primary diagnosis of asthma from 2008-2010 and transferred at any time to a pediatric intensive care bed, revealed that even more received azithromycin – over 30%. However, the length of stay for the critical care patients was unchanged whether they received azithromycin or not (both groups had a mean: 5.0 days, and median: 4.0 days). Although currently 14-30% of children admitted with acute asthma to CHAM receive azithromycin, there is currently no evidence on the efficacy of this treatment practice.

We propose to conduct the first double-blind, randomized, placebo-controlled trial to determine whether azithromycin will effect inpatient length of stay in children with acute asthma exacerbations.

OBJECTIVES

Primary Objective:

To conduct a double-blind, randomized, placebo-controlled trial to determine the clinical efficacy of azithromycin treatment in hospitalized children with acute asthma exacerbations, as measured by length of stay.

Secondary Objectives in a Subset of Patients – “Mechanism Subset Study”:

1. To quantify the relative prevalence of atypical infection in the inpatient pediatric asthma population.
2. To determine if atypical infection with *Mycoplasma pneumoniae* or *Chlamydia pneumoniae* is associated with treatment effect, if found.
3. To determine immunomodulatory effects of azithromycin in children hospitalized with acute asthma exacerbations, as measured by neutrophil counts, eosinophil counts, and interleukin-8.

Hypothesis:

Azithromycin treatment will decrease length of stay in children with persistent asthma hospitalized with acute asthma exacerbation.

OUTCOME MEASURES

Primary Outcome:

Length of Stay

Secondary Outcomes:

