The primary outcome measure is hospital length of stay (LOS). Preliminary data obtained from a Clinical Looking Glass search reveals that in 2011, there were 410 children between the ages of 4-12 years admitted to CHAM with a primary diagnosis of asthma. During their admission, 237 patients received inhaled steroids, a marker of a persistent asthma diagnosis. Using this data, the mean length of stay was 3.0 days, median 2.5 days, and standard deviation 1.6. The distribution approximated normal distribution in this group. A clinically significant difference in length of stay would be 16 hours or 0.67 days (equivalent to 0.4 standard deviations).

Data analysis will be conducted with the assistance of a statistician. LOS between the two groups will be compared using independent samples t-test, if the data is normally distributed. If the data is not normally distributed, log transformation will be attempted and if the results of the transformation yield normal distribution for both groups, then t-test will be used for the logged values and reported as a geometric mean. If log transformation is not successful in yielding normal distribution, non-parametric Mann-Whitney U test will be used to report median and interquartile ranges. All tests will be two-tailed with an $\alpha = 0.05$ to denote clinical significance.

In order determine the number of patients needed to enroll to detect a 16 hour (0.67 day) difference in length of stay with a power of 80%, PASS software was utilized, with the assistance of a statistician, to model various types of adjustments for non-parametric distribution –normal distribution adjustment, uniform distribution adjustment, and logistic distribution adjustment. For each of these adjustments, the number of patients required for enrollment per

group ranged from 83 to 96 patients. Using the largest number, 96, and assuming a 10% attrition rate for parent/guardian preference, attending preference, or safety exit criteria, the sample size will need to be 107 patients in each group. We anticipate it will take approximately 15-18 months to enroll this number of patients.

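### The parent telephone interview is the only named source for the readmission outcome, so children not reached at the final call have no one-month result, although this hospital's records could be searched for every child

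*Combined protocol and SAP*

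**What the plan says.** Under Outcome Measures, readmission is the first of seven secondary outcomes listed beneath the heading "Telephone follow-up at one week and one month". The Study Design section gives the timing, "At 7-10 days and again between 28 and 35 days after discharge", and the method: "research personnel will contact the parent/guardian of enrolled patient for a follow-up interview". The interview is to cover "days of work/school missed, hospital readmissions, emergency room visits, pediatrician visits", among other items.

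No chart or database check is named for readmission. Nothing is said about repeat call attempts, unreached families or missing outcomes. The Statistical Analysis section gives only the tests for secondary outcomes. By contrast, viral tests, chest x-rays and blood counts are explicitly to be recorded from routine care where they were done.

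Readmission appears a second time under Adverse Event Monitoring, as "readmission for asthma within 30 days". That section names no data source and does not say from which date the 30 days run.

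The plan also shows that hospital records can be searched. The background on current practice at the hospital cites azithromycin use and length of stay, with the note "Data obtained from a Clinical Looking Glass preliminary search". The Statistical Analysis section relies on the same database ("Preliminary data obtained from a Clinical Looking Glass search reveals"): for 2011 it found 410 asthma inpatients in the trial's age range and supplied length of stay and inhaled steroid use. Under Protections Against Risk, the PI keeps a list that pairs study numbers with medical record numbers.

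**The concern.** Readmission is a hard event that the treating hospital records whether or not a parent answers the telephone. As planned, it is known only for families who are reached. Two things are at stake.

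First, precision: each unreached child drops out of a comparison that already has no stated power. Second, bias: if hard-to-reach families have more unscheduled care than others, the observed rate is too low in both arms. If contact also differed by arm, the comparison itself would be distorted.

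There is a smaller mismatch of windows. The final call may fall anywhere from day 28 to day 35, so the period observed varies between families, and the earliest calls cannot confirm a 30-day result.

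Readmission matters beyond its place in the list of secondary outcomes. The Risks/Benefits section names fewer readmissions as a possible benefit to participants. The Data and Safety Monitoring Board, which meets every three months, may recommend stopping on adverse-event rates.

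**Working it through.** **The plan's own figure.** With a difference of 16/24 day, SD 1.6 days, two-sided alpha 0.05 and 80% power, the two-sample t-test needs 91.4 per group. The Mann-Whitney efficiency adjustments give:
- normal: 91.4 x pi/3 = 95.7
- uniform: 91.4 x 1 = 91.4
- logistic: 91.4 x 9/pi^2 = 83.3

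This matches the stated 83 to 96. Then 96/(1 - 0.10) = 106.7, or 107 per group. The figure reproduces, but it concerns length of stay. It is used here only as the number of children per arm.

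**Inputs not in the documents.** The contact rate and the readmission rate are not given. Everything below rests on assumed values. The unreached share u means failure of the final call, since a family missed at the first call can still report at the second. A child reached only at the first call is known up to day 7-10 and no further.

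**Loss of children and precision.** Children lost = 107 x u. The standard error grows by 1/sqrt(1 - u).

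| u (assumed) | lost per arm | left per arm | standard error multiplied by |
|---|---|---|---|
| 10% | 10.7 (11) | 96.3 | 1/sqrt(0.90) = 1.05 |
| 20% | 21.4 (21) | 85.6 | 1/sqrt(0.80) = 1.12 |
| 30% | 32.1 (32) | 74.9 | 1/sqrt(0.70) = 1.20 |

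With the same u in both arms, extreme assumptions about the unreached can move the risk difference by u either way, that is by 10 to 30 percentage points.

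**Bias in the rate, contact equal in both arms.** The observed rate is (p - u x q)/(1 - u), where p is the true rate and q is the rate among the unreached. Assume p = 8%, u = 20% and q = 20%. Then (0.08 - 0.20 x 0.20)/0.80 = 5.0%. Per arm, 107 x 0.08 = 8.6 readmissions occur, and 107 x 0.04 = 4.3 of them fall among unreached families.

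**Contact unequal by arm.** Keep p = 8% and q = 20%, and assume 10% unreached in one arm and 25% in the other:
- (0.08 - 0.10 x 0.20)/0.90 = 6.7%
- (0.08 - 0.25 x 0.20)/0.75 = 4.0%

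The difference of 2.7 points is spurious. It needs a 2.5-fold imbalance in contact.

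**Would counting an event from either source solve it?** Use the same illustration and assume half of the unreached children's readmissions are to other hospitals. Reached families contribute all their events; unreached families contribute only those at this hospital:
- 0.060 + 0.010 = 7.0%
- 0.030 + 0.025 = 5.5%

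A spurious 1.5 points would remain, and unreached children with events elsewhere would be counted as event-free. An outcome restricted to this hospital, and found the same way in every child, avoids this dependence on contact.

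**Windows.** If the 30 days run from discharge, a call on day 28 leaves two days unobserved and a call on day 29 leaves one.

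**The case against.** The strongest reply is that this is a secondary outcome in a blinded trial with an indistinguishable placebo. Contact should then be similar in the two arms, and the main cost is precision in a comparison for which no power is claimed. That stands. The unequal-contact illustration is arithmetically right, but the documents offer no mechanism for it. Even then, 6.7% of about 96 against 4.0% of about 80 is roughly 6 against 3 children, z about 0.8, far from significance.

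A reader might infer that a safety event is undercounted. The documents do not support this as a finding. Adverse Event Monitoring names no source, so it is not shown to depend on the telephone. Serious events go to the PI at once. Staff page the research team when a child with asthma is admitted, and earlier enrollment is an exclusion, so a readmission here may surface at screening while recruitment is open. None of this guarantees complete capture.

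A reader might also take the 10% attrition allowance as evidence of the gap, because its reasons do not include an unanswered call. It is not evidence: the allowance sizes an inpatient outcome that needs no call.

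Finally, it is tempting to extend the point to emergency visits, which are also known only by interview. The database searches described return admissions, length of stay, drugs given and intensive care transfer. Nothing shows that it holds emergency visits ending in discharge.

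**Conclusion.** The point holds for readmission. The interview is the only source the plan names, so a child not reached at the final call has no one-month result. A source at this hospital that does not depend on contact is already in use for planning, and it can be linked to every randomised child.

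The size is unknown because the contact rate is not given. At an assumed 10-30% unreached, about 11-32 of 107 children per arm are lost, and the standard error rises by about 5-20%. Bias in the rate arises only if unreached families differ in readmission. Bias in the comparison requires, in addition, that contact, or the way unreached families differ, varies by arm. Both are possible and neither is shown. The window mismatch is one or two days for the earliest calls, on the assumption that the 30 days are counted from discharge.

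Length of stay is unaffected. This is a cheap and worthwhile improvement to a secondary outcome; it does not threaten the trial's main conclusion.

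**What to change.** Add to the protocol:

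- For every randomised child, reached or not, search this hospital's records for readmission through day 30 after discharge. Analyse readmission to this hospital within 30 days as an outcome found identically in all children.
- Use the same search to supplement adverse-event monitoring, and state the source and starting date for the 30-day readmission event there.
- Report interview-based readmission to any hospital separately, with contact rates at each call by arm. Do not count unreached children as event-free for events elsewhere.
- Extend the search to emergency visits only if the sponsor confirms that the records hold them.
- Keep the interview for school and work days, symptoms and care received elsewhere.

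The cost is a records query and a short amendment, with no added burden on families and no change to treatment or sample size. There are three limits. Readmissions to other hospitals are still missed for unreached families. The list linking study numbers to medical record numbers must be kept until the search is done, which has to be squared with the plan to destroy identifiers as early as possible. Consent and IRB cover for a post-discharge record search must be confirmed, since the consent pages are not available for this review.
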